12.2.3 Analysis for Correlative Objectives

Correlative research analyses include examining the relationship between best clinical response/treatment outcome and PD-L1 expression in archived diagnostic tumor tissue, as well as examining the relationship between best clinical response/treatment outcome and change in soluble PD-L1 level and Th1/Th2 ratio level in serum during treatment after the 2nd dose of pembrolizumab, after each cycle of HD IL-2, relative to baseline (i.e., pre-pembrolizumab dose Day 1 of Cycle 1) and baseline microbiome diversity. PD-L1 expression can be discretized into different levels and tests such as Fisher's exact test and log-rank test will be used for its related analysis depending on the outcome types. Similar type of analyses will also be conducted to examine the change in soluble PD-L1 level, change in Th1/Th2 ratio level, arginine levels and type of intestinal microbiome at baseline.

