12.3 Sample Size and Accrual

Response rates for anti-PD-1 treatment ranges from 20%-40% [9,33-35]. Response for IL-2 in the pivotal study was 16% for melanoma [15,16]. We based our sample size calculation on the premise that response rate must be 38% or higher – otherwise the drug treatment regimen described in this protocol will be rejected (i.e., not considered further for clinical trials).

The optimal two-stage design to test the null hypothesis that $P \leq 0.260$ versus the alternative that $P \geq 0.500$ with 80% power and 0.05 level of significance proceeds as follows. After testing the drug on 11 patients, the trial will be terminated if 3 or fewer respond. If the trial goes on to the second stage, a total of 29 patients will be studied. If the total number responding is less than or equal to 11, the drug is rejected. The probability of early termination at stage 1 with a total sample size of 11 is 0.685; the probability of going on to stage 2 with a total sample size of 29 is 0.315. The sample size calculation is conducted using the software PASS 13 (NCSS, Kaysville, Utah 2014).

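### Section 12.2.3 lets scale-measured biomarkers be grouped without fixed cut-points and names only group-comparison tests; rank and continuous methods would use the same small dataset better

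*Combined protocol and SAP*

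**What the plan says.** Section 12.2.3 is the analysis plan for the correlative objectives listed in section 2.1.3. On tissue PD-L1 it states that "PD-L1 expression can be discretized into different levels", and that "tests such as Fisher's exact test and log-rank test will be used for its related analysis depending on the outcome types". It then extends the approach: "Similar type of analyses will also be conducted to examine the change in soluble PD-L1 level", followed in the same sentence by change in Th1/Th2 ratio, arginine and type of intestinal microbiome. Earlier in the section the microbiome variable is described as diversity rather than type.

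Neither section 12.2.3 nor section 8 gives a number of levels, a cut-point, a rule for choosing one, or a method that keeps a marker on its scale. Section 8.1 names the PD-L1 antibody clone (22C3) but no scoring threshold. No alpha, power or multiplicity rule is stated for these analyses.

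The sample is small. Section 12.3 says: "If the trial goes on to the second stage, a total of 29 patients will be studied". PD-L1 may be available in fewer subjects, because inclusion criterion 7 in section 3.1 requires archival tissue only where it exists.

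**The concern.** Soluble PD-L1, the Th1/Th2 ratio and arginine are quantities on a scale. Fisher's exact test and the two-sample log-rank test compare groups, so they can be applied to these markers only after the markers are cut. Two things follow if that route is taken.

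- **Information is lost.** Subjects on the same side of the cut are treated as alike, however far apart their values are. With at most 29 subjects there is little information to spare.
- **The cut is open.** If it can be set after marker and outcome data are seen, the most favourable cut can be reported and its nominal p-value no longer means what it says.

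At stake is the reliability of the exploratory signals the trial would carry forward: real associations missed, and chance ones taken up.

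**Working it through.** **1. The plan's own power figure.** The only power statement in the document is for the Simon design (section 12.3): stop if 3 or fewer of 11 respond, reject the regimen if 11 or fewer of 29 respond, with null rate 0.26 and alternative rate 0.50.

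- Early termination under the null: sum over x = 0 to 3 of C(11,x)·0.26^x·0.74^(11−x) = 0.6854 (stated 0.685).
- Probability of a positive trial: sum over x = 4 to 11 of Pr(X = x)·Pr(Y ≥ 12 − x), with X ~ Bin(11, p) and Y ~ Bin(18, p). This gives 0.0429 at p = 0.26 and 0.8075 at p = 0.50 (stated 0.05 and 80%).

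The design reproduces. It says nothing about power for the biomarker analyses.

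**2. Inputs for the biomarker check.** From the document: n = 29. Responder counts follow from the design: 0.26 × 29 ≈ 8 and 0.50 × 29 = 14.5, while 11 and 12 lie on either side of the final decision boundary. Assumed, because the document does not give them: a normally distributed marker, a mean difference of 1.0 SD between responders and non-responders, two-sided 0.05 per test, and a cut at the pooled median.

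**3. Cost of a median split in theory.** For a normal marker the asymptotic relative efficiency of a median split is 2/π = 0.637. Power after the split is Φ[(z0.975 + z_power)·√(2/π) − z0.975]. At a reference power of 80% this is Φ[(1.960 + 0.842) × 0.798 − 1.960] = Φ(0.276) = 61%. Likewise 50% falls to 35%, 70% to 51% and 90% to 73%.

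**4. Response outcome, simulated at n = 29, 1.0 SD.** With an odd sample the middle subject must go to one side of the median.

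| Responders | Middle subject | Wilcoxon | Fisher | Relative loss |
|---|---|---|---|---|
| 8 | low | 61% | 37% | 24/61 = 39% |
| 11 | low | 68% | 32% | 36/68 = 53% |
| 12 | low | 69% | 52% | 17/69 = 25% |
| 12 | high | 69% | 33% | 36/69 = 52% |
| 14 | low | 71% | 54% | 17/71 = 24% |

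At 4,000 runs the standard error near 33% is √(0.33 × 0.67/4000) = 0.7 points, so 32% and 33% are not distinguishable. With 12 responders and the middle subject in the low group, the figures are 51% against 35% at 0.8 SD, and 85% against 68% at 1.2 SD. Over a wider set of median-split settings at n = 29 (0.6 to 1.5 SD), the relative loss ran from about 10% to 62%.

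**5. How much is due to the test rather than the split.** Under no association, Fisher's actual size at a median split was 1.6 to 3.9% at n = 29; the Wilcoxon test's was about 4 to 5%. With 12 responders and the middle subject in the high group, a mid-p version of Fisher's test on the same split reaches 65% power against 69% for Wilcoxon, but with a size of 6.4%. With the middle subject in the low group, mid-p recovers nothing. So the gap is a mixture of lost information and test discreteness, in proportions that vary with the split.

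**6. Time-to-event outcome.** Further assumptions: exponential times with a median of 6 or 12 months, log hazard ratio 0.4 to 0.8 per SD, and censoring at 12 months (section 12.1 follows subjects for up to one year). Cox score test on the continuous marker against log-rank at the median: at 0.6 per SD, 71% against 50% (median 6 months) and 59% against 38% (median 12 months). The relative loss over all settings was 22 to 35%. Both tests had a size of about 5.5 to 6%, so conservatism does not explain this gap.

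**7. Choosing the cut from the data.** With no true association, taking the smallest Fisher p-value over all cuts that leave at least about 20% of subjects on each side gave a false-positive rate of about 15 to 19% at n = 29 (17.5% with 12 responders), instead of 5%. This is for one marker, one time point and one outcome.

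**The case against.** The best defence is the wording. The section says that PD-L1 can be discretized and introduces its two tests as examples, chosen according to outcome type. A reader might infer that every marker must be cut and that continuous analysis is excluded. The document does not say so; Wilcoxon and Cox analyses would be within the plan. This part of the defence stands. It does not close the matter: a plan that neither excludes a continuous analysis nor commits to one, and leaves the cut unset, allows the choice to be made after the data are seen.

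A reader might also attach one figure to the loss, such as a quarter. That does not stand either. It fits 12 or 14 responders with the middle subject in the low group; moving that one subject across the median with 12 responders takes the loss to about a half. Part of it reflects Fisher's conservatism rather than grouping.

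The scope has limits too. Type of intestinal microbiome may be categorical, in which case Fisher's test is apt. Section 8.1 gives no scoring scale for tissue PD-L1, and grouping an immunohistochemistry read-out can be defended.

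Finally, these are exploratory objectives with no decision rule. If the trial ended at 11 subjects, better methods would help little: even with 4 responders of 11, one more than the stage 1 stopping rule allows, Wilcoxon power at 1.0 SD is only about 25%. This limits the benefit but is no reason to prefer the weaker method.

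**Conclusion.** The point holds as a low-severity, nearly free improvement. Section 12.2.3 allows grouping of scale-measured markers, names only group-comparison tests and fixes no cut-points. Under the assumptions in step 2 of the working, median-split Fisher has about 33 to 54% power against about 61 to 71% for Wilcoxon, a relative loss of roughly 25 to 55% that depends on responder count and split and is partly test conservatism. A data-chosen cut brings the false-positive rate to about 15 to 19% for a single marker and outcome; this is the more serious of the two harms, because it can create findings rather than miss them.

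The documents do not support saying that the plan discretizes every marker, that a fixed share of power is lost, or that the trial's main conclusion is affected. The primary analysis and the Simon design are untouched.

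**What to change.** Amend section 12.2.3 as follows.

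- State that the main correlative analyses are the exact Wilcoxon rank-sum test for response and Cox regression on the continuous or log-transformed marker for PFS and OS. Apply these to soluble PD-L1, Th1/Th2 ratio, arginine, microbiome diversity, and tissue PD-L1 where it is scored on a scale.
- Keep Fisher's exact and log-rank tests for markers that are categorical by nature, such as microbiome type. Otherwise present grouped results as descriptive only, at cut-points fixed before marker data are linked to outcome. If the median is used, say which side the middle subject joins.

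This costs two or three sentences. It needs no new subjects, samples or assays, and leaves the sample size and stopping rule as they are.

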5.1 Pembrolizumab Administration

Subjects will receive 200 mg pembrolizumab every 3 weeks for two cycles. Cycle length is 21 days (i.e., 3 weeks). On the last day of Cycle 2 (+ 3 days), disease status will be assessed via imaging. Following the pembrolizumab treatment, HD IL-2 treatment will commence.

Correlative research analyses during pembrolizumab administration include examining the relationship between clinical response at the end of Cycle 2 with PD-L1 expression of the archived diagnostic tumor tissue. Research analyses also include examining the relationship between changes in soluble PD-L1 level and Type 1 T helper cell/Type 2 T helper cell (Th1/Th2) ratios during therapy (assessed after the 2nd dose) relative to baseline and characterization of intestinal microbiome to the best clinical response (RECIST 1.1 criteria) and to treatment outcome.

Drug	Dose	Route	Schedule	Cycle Length
Pembrolizumab	200 mg	Intravenously (IV) over 30 minutes	Day 1 of each cycle	3 weeks (21 days)

¹ A window of - 1 or + 2 days may be applied to all study visits to accommodate observed holidays, inclement weather, scheduling conflicts etc. Date and time of each drug administration should be clearly documented in subject's chart and electronic case report forms (eCRFs).

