8. BIOSPECIMEN STUDIES AND PROCEDURES

8.1 Correlate PD-L1 expression in archived diagnostic tumor tissue with best clinical response (revised RECIST criteria) and treatment outcome in subjects with stage IV malignant melanoma

Expression of PD-L1 in archived diagnostic tumor tissue will be determined by IHC by referring laboratory using anti-PD-L1 antibody clone 22C3, and will be correlated with clinical response assessed by imaging. Unstained slides are to be submitted; a tumor block is not acceptable.

8.2 Correlate the change in soluble PD-L1 and arginine levels in plasma during therapy with best clinical response (revised RECIST criteria) and treatment outcome in subjects with stage IV malignant melanoma

Whole blood for serum submission will be collected pre-dose Cycle 1 Day 1 of pembrolizumab, and on Cycle 2 Day 21 (+3 days) of pembrolizumab. Blood samples for these levels will also be collected at the end of each of the HD IL-2 cycles; End of Cycle 1 sample will be drawn prior to dosing Cycle 1 Day 5 (+3 days). The end of Cycle 2 sample will be drawn (+ 9 days) at the end of Cycle 2 Day 19 for analysis of soluble PD-L1 and arginine levels. Change in soluble PD-L1 and arginine levels as a result of treatment will be examined in relation to the best clinical response (RECIST, v1.1) and treatment outcome.

8.3 Correlate Th1/Th2 ratio and MDSCs in peripheral blood during therapy with best clinical response (revised RECIST criteria) and treatment outcome in subjects with stage IV malignant melanoma

Whole blood for serum submission will be collected pre-dose Cycle 1 Day 1 of pembrolizumab, and on Cycle 2 Day 21 (+3 days) of pembrolizumab. Blood samples for these levels will also be collected at the end of each of the HD IL-2 cycles; End of Cycle 1 sample will be drawn prior to dosing Cycle 1 Day 5 (+3 days). The end of Cycle 2 sample will be drawn (+ 9 days) at the end of Cycle 2 Day 19 for analysis of Th1/Th2 ratio levels and MDSC quantification. Change in Th1/Th2 ratio and MDSCs levels as a result of treatment will be examined in relation to the best clinical response (RECIST, v1.1) and treatment outcome.

8.4 Correlate intestinal microbiome at baseline with best clinical response (revised RECIST criteria) and treatment outcome in subjects with stage IV malignant melanoma

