9.9.5 Objective Response Rate

The objective response rate is the proportion of all subjects with confirmed PR or CR according to RECIST 1.1, from the start of treatment until disease progression/recurrence (taking as reference for progressive disease the smallest measurements recorded since the start of treatment).

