9.9.7 Progression-Free Survival

A measurement from the date of treatment initiation until the criteria for disease progression is met as defined by RECIST 1.1 or death occurs. Subjects who have not progressed will be right-censored at the date of the last disease evaluation.

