9.9.8 Overall Survival

Overall survival is defined by the date of treatment initiation to date of death from any cause.

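### Section 12.2.3 tests on-treatment marker changes against outcomes counted from first dose, so their association with day-42 response or progression has no readable direction; a landmark at each sample fixes this cheaply

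*Combined protocol and SAP*

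**What the plan says.** For archival PD-L1, section 12.2.3 says that "tests such as Fisher's exact test and log-rank test will be used for its related analysis depending on the outcome types". It then extends the approach: "Similar type of analyses will also be conducted to examine the change in soluble PD-L1 level, change in Th1/Th2 ratio level", together with arginine and the baseline microbiome. The changes are taken relative to the pre-dose sample of pembrolizumab Cycle 1, after the second pembrolizumab dose and after each HD IL-2 cycle. They are related to best response and to treatment outcome, a term the plan does not define.

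The outcomes all start at first dose:

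- PFS (9.9.7): "A measurement from the date of treatment initiation until the criteria for disease progression is met as defined by RECIST 1.1 or death occurs".
- OS (9.9.8): "Overall survival is defined by the date of treatment initiation to date of death from any cause".
- Objective response (9.9.5): counted "from the start of treatment until disease progression/recurrence".

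On timing, section 5.1 says: "On the last day of Cycle 2 (+ 3 days), disease status will be assessed via imaging". Sections 8.2 and 8.3 and footnote 7 of the study calendar put the first on-treatment blood sample in that same window, with two more around the HD IL-2 cycles. For the last: "The end of Cycle 2 sample will be drawn (+ 9 days) at the end of Cycle 2 Day 19".

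No section gives a landmark, a time-dependent covariate, a new time origin, or a rule for subjects without a sample.

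**The concern.** A baseline marker is known for everyone before the clock starts, so a test from first dose respects time order. A marker measured six to ten weeks later does not have that property. Some responses and progressions have already been recorded when the blood is drawn, and some subjects never reach the draw. A marker that merely reflects what the tumour has already done could then look as though it forecast the outcome.

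Two of the four exploratory objectives in section 2.1.3 rest on these on-treatment markers. With at most 29 subjects, a spurious association would be hard to tell from a real one.

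**Working it through.** **The plan's own figure.** No figure is given for the correlative analyses. The one design calculation, in 12.3, reproduces. P(X ≤ 3 | n = 11, p = 0.26) = 0.6854, against 0.685 stated. Summing P(X1 = x) × P(X2 ≥ 12 − x | n = 18) over x = 4 to 11 gives 0.0429 at p = 0.26 and 0.8075 at p = 0.50, consistent with the stated 0.05 and 80%. The point below does not depend on it; N = 29 is used as the full size.

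**Timeline, first dose = day 1, no delays**

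| Step | Study day |
|---|---|
| Pembrolizumab dose 2 | 1 + 21 = 22 |
| Scan and first on-treatment sample | 22 + 20 = 42, to 45 |
| HD IL-2 starts (assumed next day) | 43 |
| HD IL-2 Cycle 1 sample (Day 5, +3) | 47 to 50 |
| HD IL-2 Cycle 2 sample (Day 19, +9) | 61 to 70 |
| Restaging four weeks after HD IL-2 (5.2, 12.1) | 61 + 28 = 89 |

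Section 6.2.1 tolerates delays of up to 12 weeks, so the HD IL-2 days are not maxima. A response first met at day 42 can be confirmed at day 89, 47 days later, which satisfies the four-week minimum in 9.9.2. It then counts in best response and is tested against samples drawn 0 to 28 days (70 − 42) after it was first seen.

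**Events before the samples.** Assumption: the 46.4% six-month PFS and 68.4% 12-month OS quoted in section 1.2 for three-weekly pembrolizumab apply here, with exponential decline.

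- PFS hazard = −ln(0.464)/182.6 = 0.00421 per day. Death hazard = −ln(0.684)/365.25 = 0.00104 per day.
- Expected number by day t = 29 × (1 − exp(−hazard × t)).

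| Day | Progression or death | Death alone |
|---|---|---|
| 42 | 4.7 (16.2%) | 1.2 (4.3%) |
| 61 | 6.6 (22.6%) | 1.8 (6.1%) |
| 70 | 7.4 (25.5%) | 2.0 (7.0%) |

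A subject who has died cannot be sampled. The number with a PFS event at or before their own day 42-45 sample is therefore about 4.7 − 1.2 = 3.5, and at most 4.7.

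**Curves drawn from day 1 for sampled subjects.** If all survivors are sampled, 12-month OS would display as 0.684/(1 − 0.0615) = 72.9% for a day-61 sample, or 0.684/(1 − 0.0702) = 73.6% for day 70, rather than 68.4%. If day-42 progressors are unsampled, six-month PFS would display as about 0.464/(1 − 0.1619) = 55.4% rather than 46.4%.

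**Effect on the tests.** Simulated trials had 29 subjects, an even marker split, the rates above, scans at days 42, 89, 180, 270 and 365, and a common sample day of 65. Entries are rejection rates at the 5% level for a marker with no predictive value.

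| Situation | From first dose | Landmark |
|---|---|---|
| OS, sampled subjects | 4.3% | 4.3%, identical statistic in every trial |
| PFS, sampled subjects, day-42 progressors off therapy | 6.2% | not run |
| PFS, unsampled subjects put in the low group | 19% (OS: 6%) | not run |
| PFS, day-42 progressors sampled, marker mirrors day-42 status (shift 0.2 / 0.4) | 8% / 16% | 5% / 6% |
| Fisher test of best response, same marker (shift 0 / 0.2 / 0.4) | 3% / 9% / 33% | not run |

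The shifts, meaning changes in the probability of a high marker, are assumptions. So are the response rates used: 25% of non-progressors at day 42, and 15% of the remainder later. The last two rows keep day-42 progressors in the sampled set. They therefore fit the day 42-45 sample best, and apply to the HD IL-2 samples only if progressors continue treatment.

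**The case against.** The strongest reply is that little is biased if the plan is followed as written. Section 6.2 (Protocol Therapy Discontinuation) takes a subject with documented progression off therapy. A day-42 progressor would then have no HD IL-2 sample, and no progression can be set against a later marker value that does not exist. In that case the PFS test among sampled subjects stays near nominal (6.2%). The plan also speaks of correlation rather than prediction, its list of tests is open-ended, and the analyses are labelled exploratory.

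Most of this stands for the HD IL-2 samples. Three things survive it:

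- The day 42-45 sample shares its window with the scan, so the progression rule does not help there.
- Day-42 responders continue treatment and are sampled later, so the best-response comparison has the time-order problem at every sample.
- Sections 5.1 and 12.1 describe HD IL-2 after the day-42 scan without the progression condition in 6.2. These passages must be reconciled before anyone can say who is sampled.

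A reader might go further and infer that deaths are credited to a later measurement and that the OS test is biased. The documents do not support that. No death can precede a subject's own sample. Among sampled subjects, moving the origin by a common number of days leaves the order of events, and so the log-rank statistic, unchanged. With sample days that differ between subjects the ranks can shift, but still no death comes before its sample.

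A reader might also take the 6.6 to 7.4 of 29 modelled by days 61-70 as the number of events wrongly attributed. Under 6.2 most of these are subjects without a sample. In addition, no scan is scheduled between day 42 and restaging at about day 89, so on the quoted OS rate only about 2.0 − 1.2 = 0.8 deaths would be added to the observed events by day 70.

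**Conclusion.** The point holds in a limited form. Tests suited to a baseline marker are carried over to post-baseline changes with no landmark and no rule for missing samples.

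- **Best response:** the direction of association cannot be read, because a day-42 response precedes or coincides with all three on-treatment samples.
- **PFS against the day 42-45 sample:** about 3.5 to 4.7 of 29 subjects have their event at or before the sample, on the borrowed PFS and OS rates with exponential decline.
- **HD IL-2 samples:** the main effects are selection of subjects who get that far and guaranteed event-free time in the displayed curves. Clear test bias (19% for PFS) needs unsampled subjects to be placed in a marker group, which the plan neither proposes nor excludes.
- **OS log-rank among sampled subjects:** not biased.

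Archival PD-L1 and the baseline microbiome are untouched, and so is the primary Simon decision. This is a cheap improvement of low severity.

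**What to change.** Add one paragraph to 12.2.3 for each post-baseline marker:

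- Start the PFS and OS clocks at the scheduled sample time, and say how permitted delays move it.
- Include sampled subjects who are alive then (for OS), or alive and progression-free then (for PFS).
- Do not place unsampled subjects in a marker group; report their number and the reasons.
- Report the association with responses first met after the sample alongside the planned best-response comparison, and label the latter as not predictive.
- Keep the first-dose origin for archival PD-L1 and the baseline microbiome.

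Separately, reconcile sections 5.1 and 12.1 with section 6.2 on what follows progression at the day-42 scan. Footnote 5 of the study calendar gives a +9-day window for the post-HD IL-2 scan, while 5.2 and 12.1 give four weeks. That also needs reconciling, because it decides whether the scan coincides with the last sample.

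The cost is a few fewer subjects in each exploratory analysis. No new visit or sample is required.
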